#### **8.3.9.3.2. Columbia-Suicide Severity Rating Scale**

The PI or designee will administer the C-SSRS ([Appendix G](#)) according to the schedule in [Table 3](#). The “Baseline/Screening” version is to be completed at Visit 1 and the “Since Last Visit” version is to be completed at all subsequent scheduled timepoints. The C-SSRS should be administered by a qualified clinician trained in assessing and managing suicidal ideation and behavior ([Posner et al, 2011](#)).

### **8.3.9.4. Other Assessments**

#### **8.3.9.4.1. Cigarette Use Questionnaire**

Data on cigarette use will be collected using the question: “How many packs of cigarettes did you smoke over the past 7 days?” at the timepoints specified in [Table 3](#).

#### **8.3.9.4.2. Impact of Weight on Quality of Life – Lite**

Subjects will complete the IWQOL-Lite questionnaire ([Appendix H](#)) at the timepoints specified in [Table 3](#).

#### **8.3.9.4.3. EuroQol-5D**

Subjects will complete the EQ-5D ([Appendix I](#)) at the timepoints specified in [Table 3](#). This scale provides an indication of health status based on self-rating in the following five categories: mobility, self-care, usual activities, pain/discomfort, and anxiety/depression. Additionally, it asks subjects to rank their health status on a visual analogue scale (VAS) from “worst imaginable health state” to “best imaginable health state.”

#### **8.3.10. Rater Review**

Rater (ie, study staff) accuracy at screening on pre-specified study measures (ie, PANSS) will be reviewed by central raters.

Later reviews will take place according to a pre-specified schedule (subject to change based on rater accuracy) after the measure has been administered using an audio recording of the screening interview. Rater review is necessary for mitigating inaccurate inclusion/exclusion assessments and inaccurate efficacy assessments.

Rater assessments require subject interviews to be audio recorded. The audio recording will be disclosed and explained to the subject by study staff and will be disclosed in the ICF during the informed consent process. No subject will be recorded without the knowledge that a recording is being made.

#### **8.3.11. Laboratory Assessments**

##### **8.3.11.1. Drug Testing**

A drug screen for opioids (including codeine, hydrocodone, hydromorphone, methadone, morphine, oxycodone, and oxymorphone) and drugs of abuse (including amphetamine/methamphetamine, phencyclidine, and cocaine) will be performed at the timepoints specified in [Table 3](#). Urine drug screens may be repeated based on investigator judgment. The test may also be repeated at any time during the study, should the investigator feel it is warranted. Subjects are not eligible for participation if the results are positive at screening. If a subject is determined to be using any of these substances during the treatment period, the investigator should contact the medical monitor to discuss the course of action.

##### **8.3.11.2. Hematology, Biochemistry, and Urinalysis**

Fasting blood and urine samples will be collected at the timepoints specified in [Table 3](#) for specific hematology, biochemistry, and urinalysis assessments listed in [Table 4](#). Subjects will be instructed not to eat or drink anything (except water) for 8 hours before each visit where blood samples for biochemistry and hematology assessments will be collected. Samples will be collected in accordance with the site’s standard procedures and analyzed by a central laboratory. Laboratory assessments may be repeated at the investigator’s discretion.

**Table 4: Clinical Laboratory Assessments**

Hematology	Biochemistry	Urinalysis
Hematocrit Hemoglobin Platelet count Red blood cell count Total and differential (absolute) white blood cell count	
General Chemistry
 Albumin Bicarbonate Calcium Chloride Creatine phosphokinase Glucose Lactic dehydrogenase Potassium Sodium Total protein Uric acid	Bilirubin Color and appearance Glucose Ketones Leukocytes Nitrite Occult blood pH Protein Specific gravity Urobilinogen Cotinine
	
Endocrine Function Test
 Thyroid-stimulating hormone a HbA1c Prolactin Insulin	Microscopic examination of sediment, only if urinalysis                      dipstick results are abnormal
	
Liver Function Tests
 Alanine aminotransferase Alkaline phosphatase Aspartate aminotransferase Gamma-glutamyl transferase Total bilirubin	
	
Renal Function Tests
 Blood urea nitrogen Creatinine	
	
Lipid Panel
 High-density lipoprotein Low-density lipoprotein Total cholesterol Triglycerides	

a At screening only

**8.3.11.3. Pregnancy Testing**

A urine/serum pregnancy test will be administered to all women at the timepoints specified in [Table 3](#). At the screening visit, results must be negative for the subject to be eligible for the study. As highlighted in [Section 7.3](#) a positive pregnancy test result at any time will necessitate the subject’s immediate withdrawal from the study. Additional follow-up may be necessary as indicated in [Section 8.4.1](#)

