**Table 3: Schedule of Assessments**

Visit	Screening Day -30 to -1	24-Week Double-Blind Treatment																Safety Follow- up a		Monthly Visits b
	1	2 c	3	4	5	6	7	8	9	10	11	12	13	14	15	16	17/ET	18	19	20 to 24
Study Week (Visit Window of ±2 Days for Visits 3-24)			1	2	3	4	5	6	8	10	12	14	16	18	20	22	24	26	28	
Qualification/ Diagnostic Assessments																				
Informed Consent	X																			
Eligibility Criteria Review	X	X																		
Demographics and Medical/ Psychiatric History Review	X																			
Mini International Neuropsychiatric Interview (MINI)	X																			
Height	X																			
Qualification/ Safety Assessments																				
Serology Testing d	X																			
Pregnancy Test e	X	X									X									
Drug Screen f	X	X																		
Physical Exam g	X	X															X			
12-lead Electrocardiogram	X	X									X						X			
Abnormal Involuntary Movement Scale (AIMS)	X	X				X					X						X			
Simpson-Angus Scale (SAS)	X	X				X					X						X			
Barnes Akathisia Rating Scale (BARS)	X	X				X					X						X			

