**Table 3: Schedule of Visits and Assessments (Continued)**

Visit	Screening Day -30 to -1	24-Week Double-Blind Treatment																Safety Follow- up a		Monthly Visits b	
	1	2 c	3	4	5	6	7	8	9	10	11	12	13	14	15	16	17/ET	18	19	20 to 24	
Study Week (Visit Window of ±2 Days for Visits 3-24)			1	2	3	4	5	6	8	10	12	14	16	18	20	22	24	26	28		
Biochemistry, Urinalysis, and Hematology Samples n	X	X	X	X		X			X		X		X		X		X				
Vital Signs i	X	X	X	X		X		X	X		X		X		X		X		X		
Body Weight and Waist Circumference j	X	X	X	X		X		X	X		X		X		X		X	X	X	X j	
AE Monitoring	X	X	X	X	X	X	X	X	X	X	X	X	X	X	X	X	X	X	X	X	X k
Concomitant Medication Review l	X	X	X	X	X	X	X	X	X	X	X	X	X	X	X	X	X	X	X	X	X m
C-SSRS n	X	X	X	X	X	X	X	X	X	X	X	X	X	X	X	X	X	X	X	X	
Psychiatric Efficacy/ Lifestyle/ Quality of Life Assessments																					
PANSS o	X	X		X		X		X	X		X		X		X		X				
CGI-S	X	X		X		X		X	X		X		X		X		X				
CGI-I				X		X		X	X		X		X		X		X				
Cigarette Use Questionnaire		X				X		X	X		X		X		X		X				
IWQOL-Lite		X				X					X						X				
EQ-5D		X				X					X						X				

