**Table 3: Schedule of Visits and Assessments (Continued)**

Visit	Screening Day -30 to -1	24-Week Double-Blind Treatment																Safety Follow- up a		Monthly Visits b
	1	2 c	3	4	5	6	7	8	9	10	11	12	13	14	15	16	17/ET	18	19	20 to 24
Study Week (Visit Window of ±2 Days for Visits 3-24)			1	2	3	4	5	6	8	10	12	14	16	18	20	22	24	26	28	
Other/ General Procedures																				
Randomization		X																		
Genotype Sample	X																			
PK Labs p		X	X	X		X			X		X		X		X		X			
Study Drug Dispensation		X	X	X	X	X	X	X	X	X	X	X	X	X	X	X	X			
Study Drug Return and Adherence Review			X	X	X	X	X	X	X	X	X	X	X	X	X	X	X			
Emergency Treatment Card q		X	X	X	X	X	X	X	X	X	X	X	X	X	X	X	X			

Abbreviations: AE=adverse event; CGI-I=Clinical Global Impression-Improvement; CGI-S=Clinical Global Impression-Severity; C-SSRS=Columbia-Suicide Severity Rating Scale; ET=early termination; EQ-5D=EuroQol five dimensions questionnaire; IWQOL-Lite=Impact of Weight on Quality of Life – Lite Questionnaire; PANSS=Positive and Negative Syndrome Scale; PK=pharmacokinetics

a The Safety Follow-up Period is not required for subjects entering [ALK3831-A304](#).

b Up to 5 additional weight assessments following premature discontinuation.

c All assessments conducted at Visit 2 are to be done predose.

d Serology testing to include hepatitis B surface antigen, anti-hepatitis C antibodies, and anti-human immunodeficiency virus (HIV) antibodies. A positive hepatitis C antibody test must be confirmed by RNA testing.

e Serum pregnancy test at screening; urine pregnancy test at subsequent specified visits. The urine pregnancy test may be repeated at any time during the study based on the investigator’s judgment.

f Centralized drug testing at screening; local drug testing (via dipstick) at other timepoints. The drug panel includes opiates, amphetamine/methamphetamine, phenylcyclidine (PCP), and cocaine. The urine drug screen may be repeated at any point during the study based on the investigator’s discretion.

g Full physical exam at screening; brief physical at all other indicated visits

h Blood samples to be collected after an overnight (at least 8 hour) fast with no food or drink except water.

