## **8.4. Study Requirements and Restrictions**

### **8.4.1. Contraception and Pregnancy**

All male and female subjects must agree to use an acceptable method of contraception for the duration of the study unless they are surgically sterile or post-menopausal (see below). The following are considered acceptable methods of contraception:

1. Double-barrier protection (eg, a condom with spermicide or a diaphragm with spermicide)
2. Intrauterine device (IUD)
3. Oral contraceptive pills and other hormonal methods (eg, a vaginal ring, contraceptive patch, contraceptive implant)

Subjects who are abstinent are eligible, provided they agree to use an acceptable contraceptive method should they become sexually active.

Subjects who are surgically sterile are exempt from the requirement to use contraception. Women who have undergone a hysterectomy, bilateral tubal ligation, or bilateral salpingo-oophorectomy are considered surgically sterile. Men who have undergone a vasectomy are considered surgically sterile. Partner vasectomy is not considered an approved acceptable method of contraception for a female subject.

Women who are postmenopausal are also exempt from the requirement to use contraception. For the purpose of this study, postmenopausal is defined as the permanent cessation of menstruation for at least 12 months prior to screening in women who are 45 years of age or older.

If a subject becomes pregnant while participating in the study, she will be discontinued from study drug immediately. Pregnancies in female subjects and female partners of male subjects should be handled in the same manner. The investigator must fill out a Pregnancy Report Form and submit the information to the sponsor within 24 hours of awareness of the pregnancy, irrespective of whether an adverse event has occurred. The early termination and safety follow-up visits will be scheduled. The investigator will follow the pregnancy until completion or until pregnancy termination and notify the outcome to the sponsor. If the outcome of the pregnancy meets the criteria for immediate classification as an SAE the investigator should follow the procedure of reporting SAEs (see [Section 13.5](#)). Additional follow-up may be required.

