## **9. TREATMENT OF SUBJECTS**

### **9.1. Study Drug Dose and Administration**

Study drugs include:

- ALKS 3831 10/10 (10 mg olanzapine/10 mg samidorphan) or 20/10 (20 mg olanzapine/10 mg samidorphan) administered as a coated bilayer tablet
- Olanzapine 10 mg or 20 mg administered as a coated bilayer tablet

At Visit 2 and all subsequent visits until Visit 17 (EOT), subjects will be given blister cards containing study drug to take at home. Subjects will be instructed to take one tablet by mouth each day, preferably at bedtime. Dosing may be switched to another time at the investigator's discretion if there are tolerability problems; however, frequent switching is discouraged.

Subjects will be instructed to keep all unused tablets in their blister card and to return unused tablets to the study site at their next visit. If dosing is to occur at that visit, the dose should be taken from the subject's next blister card, not from the card they are returning.

If a dose is missed or forgotten, subjects will be instructed to resume regular dosing the following night. Subjects will be instructed not to take a double dose to try to "make up" for the missed dose.

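### Table 3 schedules no pregnancy test after Week 12, at Visit 17/ET or in follow-up; one urine test at Visit 17/ET would close most of the gap

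*Protocol*

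**What the plan says.** Section 8.3.11.3 of the protocol ties testing to the schedule: "A urine/serum pregnancy test will be administered to all women at the timepoints specified in" Table 3. It names no other timepoints. In Table 3 the "Pregnancy Test" row is marked at Visit 1 (screening), Visit 2 (baseline) and Visit 11 (Week 12). It is blank at Visits 12 to 16, 17/ET, 18, 19 and 20 to 24. Footnote e makes the screening test a serum test and later ones urine tests. It adds: "The urine pregnancy test may be repeated at any time during the study", on the investigator's judgment.

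The consequences of pregnancy are strict. Section 8.3.11.3 says that "a positive pregnancy test result at any time will necessitate the subject" to be withdrawn at once. Section 8.4.1 says: "If a subject becomes pregnant while participating in the study, she will be discontinued from study drug immediately". It also requires a report to the sponsor within 24 hours of awareness and follow-up of the pregnancy to its end.

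Dosing continues well past Week 12. Section 9.1 says: "At Visit 2 and all subsequent visits until Visit 17 (EOT), subjects will be given blister cards containing study drug". Under section 7.3 the early termination visit repeats the Visit 17 assessments. Under section 8.1 completers may enter the long-term study ALK3831-A304, and Table 3 footnote a then waives their safety follow-up.

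**The concern.** The response to a pregnancy starts only once someone knows of it. For the first half of dosing the plan includes a test that closes the period, at Week 12. For the second half it includes none. A pregnancy that neither the woman nor the investigator suspects could go unnoticed through the end of treatment, through early termination, and up to the door of A304.

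Two comparisons within the protocol make the blank at Visit 17/ET look out of pattern. First, the ECG row in Table 3 has the same early marks as the pregnancy row (Visits 1, 2 and 11) and then also 17/ET. Second, section 7.3 orders immediate discontinuation for a low neutrophil count or for HbA1c of 6.5% or more. Both are measured in the laboratory panel, which is scheduled at Visits 13, 15 and 17/ET. Those two stopping rules are therefore checked up to the end of dosing, and the pregnancy rule is not.

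At stake are late reporting and follow-up of exposed pregnancies, and possible further dosing in A304. The trial's inference is not at stake.

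**Working it through.** The plan states no figure on this point, so the check is a count of schedule marks and days.

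**Inputs**
- Pregnancy test marks: Visits 1, 2 and 11 (Table 3).
- Visit 11 = Week 12 = day 84; Visit 17 = Week 24 = day 168; each has a window of ±2 days (Table 3).
- Treatment period: 24 weeks (Synopsis, Duration of Study).
- "Study Drug Dispensation" marks: Visits 2 to 17 (Table 3).
- "Biochemistry, Urinalysis, and Hematology Samples" marks after Visit 11: Visits 13, 15 and 17/ET, i.e. Weeks 16, 20 and 24 (Table 3).

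**Is the row intact?** The pregnancy, ECG, AIMS and physical examination rows each have 20 cells, one per visit column. Read in the same way, ECG falls at Visits 1, 2, 11 and 17/ET; AIMS at 1, 2, 6, 11 and 17/ET; physical examination at 1, 2 and 17/ET. The pregnancy row is neither cut short nor shifted.

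**Dosing time after the last scheduled test**
- 168 − 84 = 84 days.
- With the windows: 166 − 86 = 80 to 170 − 82 = 88 days.
- 12 / 24 = 50% of the treatment period.

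**Dispensing after the last scheduled test.** Visits 12, 13, 14, 15 and 16 give five. The row also marks Visit 17, which makes six marks. Section 9.1 has dispensing run until Visit 17 as the end of treatment, so five is the number that supplies dosing within this study.

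**Women who stop early.** ET repeats Visit 17, which has no test. Scheduled tests after Visit 2 for a woman who stops before Week 12: 0.

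**With one test at Visit 17/ET**
- Dosing time with no later scheduled test falls from 84 days to 0, taking the last dose at about Visit 17.
- Scheduled tests at ET rise from 0 to 1.
- The longest gap between scheduled tests during dosing stays at 84 days (80 to 88), the same as the planned Visit 2 to Visit 11 gap, which is nominally 84 days.

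**With optional extra tests at Visits 13 and 15.** The gaps after Week 12 become 16 − 12, 20 − 16 and 24 − 20 = 4 weeks each, i.e. 28 days (24 to 32). 28 / 84 = one third.

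**The case against.** The strongest case on the other side is that the plan does not leave pregnancy unmanaged. Contraception is mandatory for the study's duration unless the subject is surgically sterile or postmenopausal. Women who are pregnant, breastfeeding or planning pregnancy are excluded. Screening, baseline and Week 12 tests are scheduled. After Week 6 there are visits every two weeks with adverse event and medication review. A urine test may be repeated whenever the investigator sees a reason. The documents give no number of women, no pregnancy rate and no reproductive toxicity finding, so no number of missed cases can be claimed.

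Much of this stands, and it rules out three stronger readings that a reader might infer.

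- *That nothing would detect a pregnancy after Week 12.* What is absent is a scheduled test. Detection remains possible through footnote e and routine visits, though an unsuspected pregnancy may give no reason to test.
- *That four-weekly testing is required after Week 12.* The plan accepts a gap of about 84 days before Week 12, and nothing in the documents gives a reason for a tighter interval afterwards. The frequency is a preference.
- *That contraception should continue for 60 days after the last dose, because exclusion 30 looks 60 days ahead.* Exclusion 30 concerns intentions at entry. The documents state no washout period to support a 60-day duty.

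A further objection is that a test at Visit 17/ET comes when dosing in this study has ended, so it cannot serve the immediate-discontinuation rule here. That is correct, and it limits what the fix can claim. It does not remove the value for reporting, for follow-up to outcome, or before A304. Because A304's own entry tests are not in these documents, the A304 benefit is conditional.

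**Conclusion.** The point holds as a minor gap in the safety schedule. No pregnancy test is scheduled in the last 12 of 24 dosing weeks (84 days, 80 to 88), at Visit 17/ET, or at any follow-up visit. A woman who stops before Week 12 has none after Visit 2. The plan's own duties on pregnancy then depend on awareness that no scheduled procedure after Week 12 creates.

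The day counts assume that visits fall within their windows and that the last dose is at about Visit 17. No case count or harm is claimed, since the documents give no basis for one. Endpoints, power and alpha are unaffected.

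**What to change.** In Table 3, Pregnancy Test row, add a mark at Visit 17/ET. Footnote e already makes tests after screening urine tests. Add that the result must be known before a completer enters ALK3831-A304. Because ET shares the Visit 17 column, the one mark also covers women who stop early.

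Use an on-site dipstick. Urine is already collected at that visit for urinalysis, but section 8.3.11.2 sends those samples to a central laboratory, so that analysis would not serve.

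The cost is one dipstick per woman and the kits to supply it. If the sponsor also wants to limit exposure during Weeks 12 to 24, on-site dipsticks at Visits 13 and 15, before drug is dispensed, would do so at up to two more tests per woman. That step is optional, and the documents do not establish a need for it. The contraception text in section 8.4.1 needs no change on this account.

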**8.3.11.4. Serology Testing**

A blood sample for a serology panel testing for hepatitis B surface antigen, anti-hepatitis C antibodies, and human immunodeficiency virus (HIV) will be performed at screening only (Table 3). A positive hepatitis C antibody test must be confirmed by RNA testing to be exclusionary.

**8.3.12. Pharmacokinetic Assessments**

Concentrations of olanzapine, samidorphan, and metabolites of interest will be determined from plasma samples collected according to the schedule in Table 3. The time of last study drug administration (when applicable) and the time of each PK blood draw must be documented in the subject's source documents. Samples for PK analysis will be stored at  $-20^{\circ}\text{C} \pm 10^{\circ}\text{C}$ . The PK data from these samples may be included in a subsequent population PK analysis or other post-hoc analyses conducted outside of this study.

**8.3.13. Genotype Sampling**

A blood sample may be collected (at the timepoint indicated in Table 3) for evaluation of genotypes that are potentially related to response and to explore potential genetic associations with efficacy, adverse effects, symptoms, or outcomes. No other tests will be performed with these samples.

**8.3.14. Randomization**

At the timepoint specified in Table 3, subjects will be randomized as outlined in Section 9.3.

**8.3.15. Drug Dispensation and Reconciliation**

Section 9 provides information related to drug dispensing procedures. Study drug will be dispensed at the timepoints specified in Table 3. The study drug use and storage information will be explained to/reviewed with the subject.

Whether or not samidorphan is classified as a controlled substance varies from country to country; some countries have classified samidorphan as a controlled substance, while others have not. Sites will be given storage, handling, and reconciliation instructions applicable to their country to ensure compliance with local regulations for controlled substances.

**8.3.16. Emergency Treatment Card**

An emergency treatment card will be distributed to each subject and collected from each subject at the timepoints indicated in Table 3. The card will indicate that the subject may be receiving an opioid antagonist and/or olanzapine and will include the PI's contact information, a suggested pain management plan and information regarding opiate blockade. Subjects will be instructed to keep the card with them at all times. Study personnel will confirm that subjects have the card in their possession at each study visit as indicated in Table 3.

### **8.3.17. Adverse Event Monitoring**

Adverse events will be monitored continuously from the time a subject signs the informed consent document until the completion of the final study visit (see [Table 3](#)). Adverse events and serious adverse events (SAEs) are defined in [Section 13.1](#) and [13.2](#), respectively. [Section 13.4](#) provides guidance on the monitoring and recording requirements for AEs. [Section 13.5](#) provides guidance on the reporting requirements for SAEs.

## **8.4. Study Requirements and Restrictions**

### **8.4.1. Contraception and Pregnancy**

All male and female subjects must agree to use an acceptable method of contraception for the duration of the study unless they are surgically sterile or post-menopausal (see below). The following are considered acceptable methods of contraception:

1. Double-barrier protection (eg, a condom with spermicide or a diaphragm with spermicide)
2. Intrauterine device (IUD)
3. Oral contraceptive pills and other hormonal methods (eg, a vaginal ring, contraceptive patch, contraceptive implant)

Subjects who are abstinent are eligible, provided they agree to use an acceptable contraceptive method should they become sexually active.

Subjects who are surgically sterile are exempt from the requirement to use contraception. Women who have undergone a hysterectomy, bilateral tubal ligation, or bilateral salpingo-oophorectomy are considered surgically sterile. Men who have undergone a vasectomy are considered surgically sterile. Partner vasectomy is not considered an approved acceptable method of contraception for a female subject.

Women who are postmenopausal are also exempt from the requirement to use contraception. For the purpose of this study, postmenopausal is defined as the permanent cessation of menstruation for at least 12 months prior to screening in women who are 45 years of age or older.

If a subject becomes pregnant while participating in the study, she will be discontinued from study drug immediately. Pregnancies in female subjects and female partners of male subjects should be handled in the same manner. The investigator must fill out a Pregnancy Report Form and submit the information to the sponsor within 24 hours of awareness of the pregnancy, irrespective of whether an adverse event has occurred. The early termination and safety follow-up visits will be scheduled. The investigator will follow the pregnancy until completion or until pregnancy termination and notify the outcome to the sponsor. If the outcome of the pregnancy meets the criteria for immediate classification as an SAE the investigator should follow the procedure of reporting SAEs (see [Section 13.5](#)). Additional follow-up may be required.

